Once ixazomib is reduced for any toxicity, the dose may not be re-escalated.

Rituximab and Ixazomib individually are FDA approved for NHL and multiple myeloma, respectively. The combination of a proteasome inhibitor plus anti-CD20 antibody has been studied previously.

Mechanistically, rituximab and Ixazomib does not have overlapping mechanism of action. We have in place Hepatitis screening at baseline. Rituximab does not have overlapping non-hematologic toxicity with Ixazomib. However, they will both cause cytotoxicity to hematopoietic cells, cytopenias and related increased risk for infection. We are mainly concerned for non-hematologic toxicities. Therefore, we would like to monitor peripheral neuropathy toxicities. We will stop the current dose level and consider treating patients at a lower dose level for Ixazomib if we observe at anytime that the rate of any grade of peripheral neuropathy toxicity is > 40% or the rate of grade 3 or higher peripheral neuropathy toxicity is >10%.

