### 7.1.8 Safety Analysis

Adverse event monitoring, vital signs, physical examination, 12-lead ECG, and laboratory assessments will be evaluated. Guidelines for the management for TLS are provided below in

Section 7.1.8.1. A safety analysis will be performed for all subjects participating in the study who took at least 1 dose of study drug.

For patient safety, the event of grade 3 or higher peripheral neuropathy toxicity within the first two cycles will be monitored. A rate of higher than 20% is considered excessive.

The prior probability of grade 3 or higher peripheral neuropathy toxicity is modelled by beta distribution (Beta (0.2, 0.8)). Denoting the probability of toxicity by  $p$  (TOX), the following decision criterion will be applied: We will stop the current dose level and consider treating patients at a lower dose level for Ixazomib if  $\text{Prob}\{p(\text{TOX}) > 20\% \mid \text{data}\} > 0.90$

Patients will be monitored in a cohort of 6 according to the following stopping boundaries for grade 3 or higher peripheral neuropathy toxicity.

Number of patients evaluated	Recommend stopping if $\geq$ toxicities observed
6	3-6
12	5-12
18	7-18
24	Always stop with this many patients

The operating characteristics are summarized in the following table (based on simulations from 10,000 trials).

True Toxicity Rate	Prob(stop the dose early)	Average number of patients treated
0.05	0.0023	23.96
0.10	0.0182	23.69
0.15	0.0616	23.00
0.20	0.1439	21.76

0.25	0.2677	19.97
0.30	0.4214	17.77
0.35	0.5831	15.39

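### Sections 6.4.2 and 7.1.8 set different peripheral-neuropathy limits for the same dose-stopping action without saying which governs, and the operating characteristics cover only the looser one

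*Combined protocol and SAP*

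**What the plan says.** **Section 6.4.2, text after Table 6-3.** The rule begins "We will stop the current dose level and consider treating patients at a lower dose level for Ixazomib if we observe at anytime" and has two triggers: "the rate of any grade of peripheral neuropathy toxicity is > 40"%, "or the rate of grade 3 or higher peripheral neuropathy toxicity is >10"%. It is a limit on the observed rate. It gives no minimum number of patients and no schedule of looks.

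**Section 7.1.8, Safety Analysis.** Here "the event of grade 3 or higher peripheral neuropathy toxicity within the first two cycles will be monitored", and "A rate of higher than 20% is considered excessive". With a Beta(0.2, 0.8) prior, "We will stop the current dose level and consider treating patients at a lower dose level for Ixazomib if" the posterior probability of a rate above 20% is greater than 0.90. "Patients will be monitored in a cohort of 6 according to the following stopping boundaries": at least 3 of 6, 5 of 12, or 7 of 18. A table from 10,000 simulated trials then gives the probability of stopping the dose early and the average number treated, for true rates from 0.05 to 0.35. There is no any-grade limit.

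Neither section refers to the other, and nothing elsewhere in the document sets an order between them.

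**The concern.** The action is the same in both sections, and in both the stop itself is mandatory; only treatment at a lower dose is left to be considered. The triggers differ in threshold (10% against 20%), in form (an observed proportion against a posterior probability), in window (any time against two cycles) and in timing (continuous against cohorts of six).

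The different windows do not reconcile them, because every grade 3 or higher event in cycles 1 and 2 also counts under the any-time rule.

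With 2 of 6 patients affected, the observed rate is 33%. Section 6.4.2 requires the 4 mg level to stop, while the Section 7.1.8 boundary has not been reached. A team working from Section 7.1.8 would carry on. An oversight reader of that section would also believe that a stop is very unlikely when toxicity is low, which is not so if Section 6.4.2 is followed.

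**Working it through.** **Inputs.** From Section 7.1.8: prior Beta(0.2, 0.8), limit 20%, cut-off 0.90, looks at 6, 12 and 18. From Section 7.1.1: maximum 24 patients. From Section 6.4.2: observed-rate limits of 10% (grade 3 or higher) and 40% (any grade).

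**1. Reproduce the Section 7.1.8 boundaries.** With x events in n patients, the posterior is Beta(0.2 + x, 0.8 + n − x). The rule stops at the smallest x for which Prob(rate > 0.20) > 0.90.

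| n | Posterior probability at the boundary | One event fewer |
|---|---|---|
| 6 | 3 events: 0.928 | 2 events: 0.721 |
| 12 | 5 events: 0.943 | 4 events: 0.829 |
| 18 | 7 events: 0.959 | 6 events: 0.888 |

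The printed boundaries are correct.

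**2. Reproduce the table.** I used an exact binomial recursion over looks at 6, 12 and 18. At a true 10%, the stop probabilities at the three looks are 0.01585, 0.00204 and 0.00036, which sum to 0.0182. Average number: 6 × 0.01585 + 12 × 0.00204 + 18 × 0.00036 + 24 × 0.98175 = 23.69. All seven rows match to the printed digits with these boundaries alone, so the Section 6.4.2 limits are not in the table.

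**3. Put the two rules side by side on grade 3 or higher events.** An observed rate above 10% means at least 1 of 6 (16.7%), 2 of 12 (16.7%) or 2 of 18 (11.1%).

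| Look | Section 6.4.2 stops at | Section 7.1.8 stops at | Rules disagree at | Chance of disagreement, true 5% | True 10% |
|---|---|---|---|---|---|
| 6 | ≥1 | ≥3 | 1–2 | 0.26 | 0.45 |
| 12 | ≥2 | ≥5 | 2–4 | 0.12 | 0.34 |
| 18 | ≥2 | ≥7 | 2–6 | 0.23 | 0.55 |

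The last two columns are binomial probabilities at each look, ignoring earlier stops.

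**4. Operating characteristics of the 10% limit.** The recursion is the same, counting stops before patient 24. Because the protocol gives no look schedule, three readings are shown. The start at 10 patients is my assumption, chosen as a lenient reading. Worked example, true 10%, looks at 6, 12 and 18: the first look stops with probability 1 − 0.9⁶ = 0.4686, the second adds 0.0607 and the third 0.1205, total 0.6498. Average number: 6 × 0.4686 + 12 × 0.0607 + 18 × 0.1205 + 24 × 0.3502 = 14.1.

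Each cell gives the probability of stopping early, with the average number treated at the dose level in brackets.

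| True grade ≥3 rate | Printed table | Every patient from n = 10 | Looks 6, 12, 18 | Every patient from n = 1 |
|---|---|---|---|---|
| 5% | 0.0023 (23.96) | 0.25 (21.4) | 0.35 (18.6) | 0.43 (16.4) |
| 10% | 0.0182 (23.69) | 0.60 (17.4) | 0.65 (14.1) | 0.72 (11.1) |
| 20% | 0.1439 (21.76) | 0.93 (12.3) | 0.93 (9.0) | 0.96 (5.6) |

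**5. The any-grade limit.** At a true any-grade rate of 20%, the 40% limit alone stops early with probability 0.09 / 0.13 / 0.43 under the three readings, in the same order. Both Section 6.4.2 limits together, at 5% grade 3 or higher and 20% any grade (trinomial recursion), give 0.29 / 0.40 / 0.62.

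**6. Is Section 7.1.8 redundant if both rules run?** Its smallest trigger is 3 events. Even over all 24 patients that is 3/24 = 12.5%, above 10%. As written, with no minimum number, Section 6.4.2 therefore fires first or at the same time. Only an added minimum, such as 10 patients, would let 3 of 6 trigger Section 7.1.8 first.

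**The case against.** The best defence is that each section gives a sufficient condition for stopping, and Section 7.1.8 nowhere orders continuation below 3 of 6. Read literally, 2 of 6 meets Section 6.4.2 and the dose level stops. That reading also errs towards protecting patients. It is a tenable reading, but the protocol does not state it. If it is adopted, the Bayesian rule becomes redundant and its table no longer describes the trial being run.

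Several narrower points stand:

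- The action stops a dose level, with 3.0 mg or 2.3 mg to follow. The averages above are patients treated at the current level, not trial size.
- The denominator can be inferred from Sections 7.1 and 7.1.8 as patients who received at least one dose. What remains open is the minimum number and how to count patients still under observation.
- The table is correct for the boundaries printed above it.
- The any-grade limit does not contradict Section 7.1.8, which is silent on it; it simply has no operating characteristics.
- Table 6-3 still governs each individual patient.

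True rates may also lie below 5%. Section 1.3 reports no grade 3–4 neuropathy with a bortezomib combination, and Section 5.2 excludes patients with marked baseline neuropathy. That is a different agent and regimen, so it is only suggestive. At a true 1%, the 10% limit stops early with probability 0.015 / 0.064 / 0.090 under the three readings; at 2%, 0.055 / 0.135 / 0.180. The gap is smaller in absolute terms, but these values still exceed the 0.0023 printed for a true 5%.

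**Conclusion.** The concern holds. The protocol ties one mandatory action to two different grade 3 or higher limits with no precedence, and its only operating characteristics for neuropathy describe the looser one. At a true 5%, early stopping is 0.25 to 0.43 under the 10% limit against 0.0023 in the table; at 20% it is 0.93 to 0.96 against 0.1439. Even the most lenient reading gives roughly 100 times the printed value at 5% (0.2508/0.0023 ≈ 109) and over 30 times at 10% (0.5951/0.0182 ≈ 33).

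The figures assume that the rate is the raw proportion among treated patients, that outcomes are known at each look, and that the event probability is the same in both windows. Events after cycle 2 can only add to the Section 6.4.2 count. The efficacy analysis and the sample-size statement do not depend on this table; what is affected is the cohort-level dose decision and what readers are told about it.

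**What to change.** Put one governing neuropathy rule in both sections, giving the grades, thresholds, observation window, denominator, and the looks or minimum number of patients. Alternatively, state in both places that the two rules apply together and that the dose level stops when either fires. Then recompute the boundary and operating-characteristics tables for the rule or rules in force, including the any-grade limit if it is kept. The choice between 10% and 20% is clinical and belongs to the study team.

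The cost is a wording amendment and one simulation run, with no added patients or procedures. If the 10% limit stays, the protocol will have to report a much higher chance of stopping the dose level early than it does now.

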#### **6.4.3 Recommended Dose Modifications for Rituximab Treatment Associated Toxicity**

There will be no dose reductions for rituximab. However, the rate of infusion may be reduced for patients experiencing hypersensitivity reaction.

### **Excluded Concomitant Medications and Procedures**

The following medications and procedures are prohibited during the study.

Systemic treatment with any of the following metabolizing enzyme inducers should be avoided, unless there is no appropriate alternative medication for the patient's use (Rationale: If there were to be a drug-drug interaction with an inducer, ixazomib exposure would be decreased):

- Strong CYP3A inducers: rifampin, rifapentine, rifabutin, carbamazepine, phenytoin, and phenobarbital

The following medicinal products and procedures are prohibited during the study.

- Excluded foods and dietary supplements include St. John's wort.
- Any antineoplastic treatment with activity against MCL, other than study drugs
- Radiation therapy (note that, in general, the requirement for local radiation therapy indicates disease progression)
- Platelet transfusions to help patients meet eligibility criteria are not allowed within 3 days prior to study drug dosing for any dosing day

### **6.5 Permitted Concomitant Medications and Procedures**

The following medications and procedures are permitted during the study:

- Antiemetics, including 5-HT3 serotonin receptor antagonists, may be used at the discretion of the investigator.
- Loperamide or other antidiarrheal should be used for symptomatic diarrhea at discretion of the investigator. The dose and regimen will be according to institutional guidelines. IVF should be given to prevent volume depletion.
- Growth factors (e.g., granulocyte colony stimulating factor [G-CSF], granulocyte macrophage-colony stimulating factor [GM-CSF], recombinant erythropoietin) are permitted. Their use should follow published guidelines and/or institutional practice; however, alternative usage may be reviewed with the Millennium Clinical or Medical Representative. Erythropoietin will be allowed in this study. Their use should follow published guidelines and/or institutional practice.

- Patients should be transfused with red cells and platelets as clinically indicated and according to institutional guidelines.
- Antiviral therapy such as acyclovir may be administered if medically appropriate.
- Concomitant treatment with bisphosphonates will be permitted, as appropriate.
- Patients who experience worsening neuropathy from baseline may be observed for recovery, and have dose reductions/delays as indicated in the protocol, and any supportive therapy or intervention may be initiated as appropriate at the discretion of the investigator.
- Supportive measures consistent with optimal patient care may be given throughout the study.

## 6.6 Precautions and Restrictions

- Fluid deficit should be corrected before initiation of treatment and during treatment.
- Nonsteroidal anti-inflammatory drugs (NSAIDs) should be avoided with impaired renal function given reported NSAID-induced renal failure in patients with decreased renal function.

### Pregnancy

It is not known what effects ixazomib has on human pregnancy or development of the embryo or fetus. Therefore, female patients participating in this study should avoid becoming pregnant, and male patients should avoid impregnating a female partner. Nonsterilized female patients of reproductive age group and male patients should use effective methods of contraception through defined periods during and after study treatment as specified below.

Female patients must meet 1 of the following:

- Postmenopausal for at least 1 year before the screening visit, or
- Surgically sterile, or
- If they are of childbearing potential, agree to practice 2 effective methods of contraception from the time of signing of the informed consent form through 90 days after the last dose of study drug, or

- Agree to practice true abstinence, when this is in line with the preferred and usual lifestyle of the subject. (Periodic abstinence [e.g., calendar, ovulation, symptothermal, postovulation methods] and withdrawal are not acceptable methods of contraception.)

Male patients, even if surgically sterilized (i.e., status postvasectomy) must agree to 1 of the following:

- Practice effective barrier contraception during the entire study treatment period and through 90 days after the last dose of study drug, or
- Agree to practice true abstinence, when this is in line with the preferred and usual lifestyle of the subject. (Periodic abstinence [e.g., calendar, ovulation, symptothermal, postovulation methods for the female partner] and withdrawal are not acceptable methods of contraception.)

## **6.7 Management of Clinical Events**

Adverse drug reactions such as thrombocytopenia, diarrhea, fatigue, nausea, vomiting, and rash have been associated with ixazomib treatment. Management guidelines regarding these events are outlined below. Further details of management of ixazomib AEs are described in Section 6 of the ixazomib IB.

### **Prophylaxis Against Risk of Reactivation of Herpes Infection**

Patients may be at an increased risk of infection including reactivation of herpes zoster and herpes simplex viruses. Antiviral therapy such as acyclovir, valacyclovir, or other antivirals may be initiated as clinically indicated. Other antivirals are also acceptable.

### **Nausea and/or Vomiting**

Standard anti-emetics including 5-hydroxytryptamine 3 serotonin receptor antagonists are recommended for emesis if it occurs once treatment is initiated; prophylactic anti-emetics may also be considered at the physician's discretion. Dexamethasone should not be administered as an anti-emetic. Fluid deficit should be corrected before initiation of study drug and during treatment.

### **Diarrhea**

Prophylactic antidiarrheals will not be used in this protocol. However, diarrhea should be managed according to clinical practice, including the administration of antidiarrheals once

infectious causes are excluded. Fluid intake should be maintained to avoid dehydration. Fluid deficit should be corrected before initiation of treatment and during treatment.

### **Erythematous Rash With or Without Pruritus**

As with bortezomib, rash with or without pruritus has been reported with ixazomib, primarily at the higher doses tested and when given with agents where rash is an overlapping toxicity. The rash may range from limited erythematous areas, macular and/or small papular bumps that may or may not be pruritic over a few areas of the body, to a more generalized eruption that is predominately on the trunk or extremities. Rash has been most commonly characterized as maculopapular or macular. To date, when it does occur, rash is most commonly reported within the first 3 cycles of therapy. The rash is often transient, self-limiting, and is typically Grade 1 to 2 in severity.

Symptomatic measures such as antihistamines or corticosteroids (oral or topical) have been successfully used to manage rash and have been used prophylactically in subsequent cycles. The use of a topical, IV, or oral steroid (e.g., prednisone  $\leq$  10 mg per day or equivalent) is permitted. Management of a Grade 3 rash may require intravenous antihistamines or corticosteroids. Administration of ixazomib (and/or other causative agent if given in combination) should be modified per protocol and re-initiated at a reduced level from where rash was noted (also, per protocol).

In line with clinical practice, dermatology consult and biopsy of Grade 3 or higher rash or any SAE involving rash is recommended. Prophylactic measures should also be considered if a patient has previously developed a rash (e.g., using a thick, alcohol-free emollient cream on dry areas of the body or oral or topical antihistamines). A rare risk is Stevens-Johnson Syndrome, a severe and potentially life-threatening rash with skin peeling and mouth sores, which should be managed symptomatically according to standard medical practice. Punch biopsies for histopathological analysis are encouraged at the discretion of the investigator.

### **Thrombocytopenia**

Blood counts should be monitored regularly as outlined in the protocol with additional testing obtained according to standard clinical practice. Thrombocytopenia may be severe but has been manageable with platelet transfusions according to standard clinical practice. Ixazomib administration should be modified as noted as per dose modification recommendations in the protocol when thrombocytopenia occurs (see Table 6-2). Therapy can be reinitiated at a reduced level upon recovery of platelet counts. A rare risk is thrombotic thrombocytopenic purpura (TTP), a rare blood disorder where blood clots form in small blood vessels throughout the body

characterized by thrombocytopenia, petechiae, fever, or possibly more serious signs and symptoms. TTP should be managed symptomatically according to standard medical practice.

### **Neutropenia**

Blood counts should be monitored regularly as outlined in the protocol with additional testing obtained according to standard clinical practice. Neutropenia may be severe but has been manageable. Growth factor support is not required but may be considered according to standard clinical practice. Ixazomib administration should be modified as noted as per dose modification recommendations in the protocol when neutropenia occurs (see Table 6-2). Therapy can be reinitiated at a reduced level upon recovery of ANCs.

### **Fluid Deficit**

Dehydration should be avoided since ixazomib may cause vomiting, diarrhea, and dehydration. Acute renal failure has been reported in patients treated with ixazomib, commonly in the setting of the previously noted gastrointestinal toxicities and dehydration.

Fluid deficit should be corrected before initiation of study drug and as needed during treatment to avoid dehydration.

### **Hypotension**

Symptomatic hypotension and orthostatic hypotension with or without syncope have been reported with ixazomib. Blood pressure should be closely monitored while the patient is on study treatment and fluid deficit should be corrected as needed, especially in the setting of concomitant symptoms such as nausea, vomiting, diarrhea, or anorexia. Patients taking medications and/or diuretics to manage their blood pressure (for either hypo- or hypertension) should be managed according to standard clinical practice, including considerations for dose adjustments of their concomitant medications during the course of the trial. Fluid deficit should be corrected before initiation of study drug and as needed during treatment to avoid dehydration.

### **Posterior Reversible Encephalopathy Syndrome**

One case of posterior reversible encephalopathy syndrome, which ultimately resolved, has been reported with ixazomib. This condition is characterized by headache, seizures and visual loss, as well as abrupt increase in blood pressure. Diagnosis may be confirmed by magnetic resonance imaging (MRI). If the syndrome is diagnosed or suspected, symptom-directed treatment should be maintained until the condition is reversed by control of hypertension or other instigating factors.

### **Transverse Myelitis**

Transverse myelitis has also been reported with ixazomib. It is not known if ixazomib causes transverse myelitis; however, because it happened to a patient receiving ixazomib, the possibility that ixazomib may have contributed to transverse myelitis cannot be excluded.

## **6.8 Preparation, Reconstitution, and Dispensing**

Ixazomib is an anticancer drug and as with other potentially toxic compounds caution should be exercised when handling ixazomib capsules.

### **Rituximab**

Use appropriate aseptic technique. Parenteral drug products should be inspected visually for particulate matter and discoloration prior to administration. Rituximab should be a clear, colorless liquid. Do not use vial if particulates or discoloration is present. Administration  
Withdraw the necessary amount of rituximab and dilute to a final concentration of 1 mg/mL to 4 mg/mL in an infusion bag containing either 0.9% Sodium Chloride, USP, or 5% Dextrose in Water, USP. Gently invert the bag to mix the solution. Do not mix or dilute with other drugs. Discard any unused portion left in the vial. Storage rituximab solutions for infusion may be stored at 2°C–8°C (36°F–46°F) for 24 hours. rituximab solutions for infusion have been shown to be stable for an additional 24 hours at room temperature. However, since rituximab solutions do not contain a preservative, diluted solutions should be stored refrigerated (2°C–8°C). No incompatibilities between rituximab and polyvinylchloride or polyethylene bags have been observed.

